Additionally, enrollment into the study and study vaccination will be halted pending review by the DSMB if during Day 1 to Day 7, the following defined halting rule criteria are met in either study cohort (6 months through 35 months or 36 months through 59 months):

- $\geq 5\%$ of subjects enrolled to date with concurrent grade 3 pain, erythema, and induration (a cellulitis-like reaction) that is assessed as related to Study Vaccine.
(Note: If the total number of subjects enrolled to date is less than 60, a minimum of 3 subjects experiencing a concurrent severe vaccine-associated pain, erythema or induration will be needed to halt further enrollment);
- $\geq 5\%$ of subjects enrolled to date, experience a fever of $\geq 101.3^{\circ}\text{F}$ [$\geq 38.5^{\circ}\text{C}$] (axillary) that is assessed as related to Study Vaccine.
(Note: if the total number of subjects enrolled to date is less than 60, a minimum of 3 subjects is required to trigger the halt).

In addition, the DSMB chair will be immediately notified of any SAE, regardless of causality or expectedness assessment, occurring during Day 1 to Day 7. The DSMB chair will then make a determination regarding the necessity of a DSMB meeting and/or study halt in response to these events.

Data Safety Monitoring Board

An independent DSMB will monitor subject safety during the study. The DSMB will comprise clinical study experts with experience in vaccine studies and safety assessment. The DSMB will provide recommendations for stopping or continuing the study based on the assessment of study safety data according to processes defined in the study protocol and the DSMB Charter.

Schedule of Assessments – Single Dose Regimen

Assessment		Visit 1	Phone call	Visit 2	Phone call	Phone call
	Pre-Study	Vaccination	Diaries Reminder	Exit Visit	SAE Follow-up	SAE Follow-up
	Day -7 to -1	Day 1	Day 3 + 2	Day 29 + 4	Day 90 + 7	Day 180 + 7
Invitation to participate		✓ ¹				
Informed consent		✓ ¹				
Demographics and influenza vaccination history		✓ ¹				
Medical history and baseline medication use		✓ ¹				
Targeted physical examination (if necessary)		✓ ¹		✓		
Body weight		✓ ¹				
Axillary temperature		✓				
Review of eligibility criteria		✓				
Blood sample for immunogenicity testing		✓		✓		
Vaccination		✓				
Provision of study supplies and instructions		✓				
Solicited Diary review			✓	✓		
Unsolicited/Concomitant Medications Diary review			✓	✓		
Assessment for cellulitis-like reaction, influenza-like illness (if applicable) ²		← ✓ →				
Review of adverse events and concomitant medications	← ✓ →					
Review of SAEs and AESIs (if applicable)	← ✓ →					

Notes to the schedule of assessments:

¹ These may be performed on or up to 7 days before the day of vaccination.

² Elevated axillary temperature of $\geq 99.5^{\circ}\text{F}$ ($\geq 37.5^{\circ}\text{C}$) (or a clear history of fever/chills), and at least one respiratory symptom (including sore throat, cough, wheezing, rhinorrhea/rhinitis) and at least one systemic symptom (including myalgia, headache, malaise and fatigue, diarrhea, nausea and/or vomiting, loss of appetite, and irritability).

Schedule of Assessments – Two Dose Regimen

Assessment		Visit 1	Phone call	Visit 2	Phone call	Visit 3	Phone call	Phone call
	Pre-Study	Vaccination	Diaries Reminder	Vaccination	Diaries Reminder	Exit Visit	SAE Follow-up	SAE Follow-up
	Day -7 to -1	Day 1	Day 3 + 2	Day 29 + 4	Day 3 + 2 after 2 nd dose	Day 29 + 4 after 2 nd dose	Day 90 + 7 after 2 nd dose	Day 180 + 7 after 2 nd dose
Invitation to participate	✓ ¹							
Informed consent	✓ ¹							
Demographics and influenza vaccination history	✓ ¹							
Medical history and baseline medication use	✓ ¹							
Targeted physical examination (if necessary)	✓ ¹			✓		✓		
Body weight	✓ ¹							
Axillary temperature		✓		✓				
Review of eligibility criteria		✓		✓				
Blood sample for immunogenicity testing		✓				✓		
Vaccination		✓		✓				
Provision of study supplies and instructions		✓		✓				
Solicited Diary review			✓	✓	✓	✓		
Unsolicited/Concomitant Medications Diary review			✓	✓	✓	✓		
Assessment for cellulitis-like reaction, influenza-like illness (if applicable) ²		←————— ✓ —————→						
Review of adverse events and concomitant medications		←————— ✓ —————→						
Review of SAEs and AESIs (if applicable)		←————— ✓ —————→						

Notes to the schedule of assessments: ¹ These may be performed on or up to 7 days before the day of vaccination. ² Elevated axillary temperature of $\geq 99.5^{\circ}\text{F}$ ($\geq 37.5^{\circ}\text{C}$) (or a clear history of fever/chills), and at least one respiratory symptom (including sore throat, cough, wheezing, rhinorrhea/rhinitis) and at least one systemic symptom (including myalgia, headache, malaise and fatigue, diarrhea, nausea and/or vomiting, loss of appetite, and irritability).

TABLE OF CONTENTS

Protocol Synopsis.....5

TABLE OF CONTENTS.....27

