Subjects in the 36 through 59 months age cohort will be enrolled and randomized first until approximately one third of subjects (or a minimum of 300 subjects) in this age cohort have received the first vaccination and have had an opportunity to enter at least 7 days of safety data postvaccination. A safety data cut will then be performed and a Data and Safety Monitoring Board (DSMB) meeting convened to review and assess the available safety data.

Recruitment in the 36 through 59 months age cohort will not be halted during the period of the data cut and DSMB review. Enrollment in the younger age cohort (subjects 6 months through 35 months of age) will only commence after the DSMB has reviewed the safety data and recommended that the study may proceed.

A second safety data cut will be performed when approximately one third of subjects (or a minimum of 300 subjects) in the 6

through to 35 months age cohort have received the first vaccination and have had an opportunity to enter at least the 7 days of safety data postvaccination, A DSMB meeting will be convened to review and assess the available safety data. Recruitment in the 6 through 35 months age cohort will not be halted during the period of the data cut and DSMB review.

After stratification, subjects will be randomized to one of the two treatment groups using a 3:1 allocation ratio to receive either Seqirus QIV or the US licensed comparator QIV.

Subjects will provide pre- and postvaccination serological specimens as well as structured safety follow-up.

Screening evaluations will be performed either the day of the vaccination or within a maximum of 1 week before vaccination and include medical history, and targeted physical examination (if clinically indicated). Vaccination will occur on Day 1. On Day 1 and prior to vaccination, a serum sample will be collected for influenza-specific serology.

The parent(s)/guardian(s) of subjects will record electronically:

1. In a “7-Day Diary”: the occurrence of solicited AEs, a pre-specified series of local reactions and systemic symptoms and temperature that may occur between Day 1 and Day 7 after a vaccination.
2. In an “Other Body Symptoms Diary”, any unsolicited AEs that may occur between Day 1 and the Study Exit Visit.
3. In a “Medication Diary”, all concomitant medication use that may occur between Day 1 and the Study Exit Visit.

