Pharmacokinetics	Not Applicable.
Pharmacodynamics	Not Applicable.
Other Assessments	Not Applicable.
Statistical Analyses	
Primary Immunogenicity Analysis
 
The primary objective is to demonstrate that vaccination with Seqirus QIV elicits a noninferior immune response compared to a US licensed comparator QIV among a pediatric population 6 months through 59 months of age.
 
Co-primary immunogenicity endpoints of geometric mean titer (GMT) and seroconversion rate for each virus strain contained in the vaccine will be assessed. The rate of seroconversion is defined as the percentage of subjects with either a prevaccination hemagglutinin inhibition (HI) titer < 1:10 and a postvaccination HI titer ≥ 1:40 or a prevaccination titer ≥ 1:10 and a ≥ 4-fold increase in postvaccination titer.
 
The noninferiority of Seqirus QIV compared to the US licensed comparator QIV will be assessed by the 8 co-primary endpoints of GMT and seroconversion rate.
 
In line with the FDA Guidance on seasonal inactivated influenza vaccines (Guidance for Industry Clinical Data Needed to Support Licensure of Seasonal Inactivated Influenza Vaccines 2007) Seqirus QIV will be considered to be noninferior to the US licensed comparator QIV for each strain if:
 
 • The upper bound of the two-sided 95% confidence interval (CI) on the ratio of the GMTs does not exceed 1.5. The GMT ratio will be calculated by $\text{GMT}_{\text{Comparator QIV}} / \text{GMT}_{\text{Seqirus QIV}}$ • The upper bound of the two-sided 95% CI on the difference between the seroconversion rates does not exceed 10%. The difference in seroconversion rate will be calculated by $(\text{Seroconversion}_{\text{Comparator QIV}} - \text{Seroconversion}_{\text{Seqirus QIV}})$. 
To determine the GMT ratio (adjusted analysis) a general linear

model (GLM) will be fitted on log transformed postvaccination HI titer (titer) as the outcome variable and with inclusion of covariates such as vaccine treatment, prevaccination HI titer, age stratum, sex, vaccination history, age-by-vaccine interaction and study site.

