From the model an adjusted difference in least square means (on the log scale) will be produced with 95% confidence limits. The estimated difference and the confidence limits will be back transformed to obtain an *adjusted GMT ratio* with 95% confidence limits. Each of the four strains will be analyzed separately. The adjusted GMT ratio will be the result for which the noninferiority assessment will be based on. The measure of the *unadjusted* GMT ratio based on postvaccination GMTs only will also be presented.

Secondary Objectives:

Secondary objectives include assessing the safety and tolerability of Seqirus QIV in two age strata: 6 months through 35 months and 36 months through 59 months of age, as well as overall.

The proportion of subjects with AEs in the two treatment arms will be presented. Adverse events will be monitored postvaccination as per the following:

1. Solicited local adverse reactions and systemic AEs through Day 7 (Days 1, 2, 3, 4, 5, 6, 7) after each vaccination dose;
2. Cellulitis-like reaction and cellulitis for 28 days after each vaccination dose;
3. Unsolicited AEs for at least 28 days following each vaccination dose;
4. Serious adverse events (SAEs) for at least 180 days following the last vaccination dose.

The frequency, duration and intensity of solicited and unsolicited AEs will be summarized for each age group and study vaccine. The proportion of subjects reporting each type of AE will be presented along with percentages and confidence intervals. Solicited local adverse reactions and systemic AEs will be summarized by frequency, duration and intensity. Unsolicited AEs will be summarized by body system and intensity. If sufficient numbers of cases of AEs occur, more formal statistical analyses of event rates or intensity may be conducted.

Further details of planned analyses will be specified in the Statistical Analysis Plan (SAP).

Statistical Considerations for Sample Size Calculations:

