Seqirus QIV will be tested against a US licensed comparator QIV. The treatment randomization ratio is 3:1 (Seqirus QIV: Comparator QIV). This study is designed to achieve at least 80% power to demonstrate noninferiority for all of the 8 co-primary endpoints, seroconversion rates for 4 strains, GMT for 4 strains using a one-sided alpha of 0.025 for each comparison. No adjustment for multiple endpoints was made. For comparisons of SCR a noninferiority margin of 10% (Seqirus QIV - Comparator QIV) will be employed. It is assumed that the SCR for all strains for QIV is 50% and that there is no difference between Seqirus QIV and Comparator QIV.

For comparison of GMT ratio a noninferiority margin of 1.5 (Comparator QIV/ Seqirus QIV, equivalent to a difference on the log scale of 0.405465108) will be employed. It is assumed that there is no difference between Seqirus QIV and Comparator QIV (ie, a ratio of 1, difference on the log scale of 0) and that the standard deviation of log (titer) is 1.4.

Under these assumptions and with n evaluable = 1500 in the Seqirus QIV group and 500 in the Comparator QIV the power for 4 GMT ratio endpoints is 99.95% and the power for 4 SCR endpoints is 89.70%. The overall global power of the 8 endpoints is then $89.7\% \times 99.95\% = 89.66\%$. This provides a total N evaluable = 2000 (with 10% dropouts N=2222). Sample size calculations were performed using SAS v9.3.

Interim Analyses

An interim analysis will be made once all subjects have completed all immunogenicity assessments and all solicited and unsolicited adverse event reporting.

Enrollment Halting Rules

Enrollment into the study and study vaccination will be halted for DSMB review/ recommendation for continuation if during the 7 days after vaccination (Day 1 to Day 7) any of the following occur:

- One or more subject experiences an AE that is serious, unexpected, and is assessed as related to Study Vaccine;
- One or more subject experiences an AE that is life-threatening or causes death;
- One or more subject experiences a serious febrile AE, defined as any AE meeting seriousness criteria that is also associated with a fever of $\geq 101.3^{\circ}\text{F}$ / $\geq 38.5^{\circ}\text{C}$ (axillary);
- One or more of the subjects experiences a severe (grade 3)

- allergic reaction (eg, hives, angioedema, allergic asthma, systemic anaphylaxis);
- Vaccine-related injection site ulceration, abscess, or necrosis;

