11 STATISTICS

11.1 SAMPLE SIZE ESTIMATION

Statistical considerations for sample size calculations:

Seqirus QIV will be tested against a US licensed comparator QIV. The treatment randomization ratio is 3:1 (Seqirus QIV: Comparator QIV). This study is designed to achieve at least 80% power to demonstrate noninferiority for all of the 8 co-primary endpoints, seroconversion rates for 4 strains, GMT for 4 strains using a one-sided alpha of 0.025 for each comparison. No adjustment for multiple endpoints was made. For comparisons of SCR a noninferiority margin of 10% (Seqirus QIV - Comparator QIV) will be employed. It is assumed that the SCR for all strains for QIV is 50% and that there is no difference between Seqirus QIV and Comparator QIV.

For comparison of GMT ratio a noninferiority margin of 1.5 (Comparator QIV/ Seqirus QIV, equivalent to a difference on the log scale of 0.405465108) will be employed. It is assumed that there is no difference between Seqirus QIV and Comparator QIV (ie, a ratio of 1, difference on the log scale of 0) and that the standard deviation of log (titer) is 1.4.

Under these assumptions and with n evaluable = 1500 in the Seqirus QIV group and 500 in the Comparator QIV the power for 4 GMT ratio endpoints is 99.95% and the power for 4 SCR endpoints is 89.70%. The overall global power of the 8 endpoints is then $89.7\% \times 99.95\% = 89.66\%$.

This provides a total N evaluable = 2000 (with 10% dropouts N=2222). Sample size calculations were performed using SAS v9.3 and PASS v12.0.02.

[Table 11.1-1](#) summarises the list of all primary endpoints with strains, the planned noninferiority margin and underlying assumptions used for the sample size computations.

Table 11.1-1: Summary of Assumptions Used for Sample Size Calculations

	H1N1	H3N2	B strains
Test significance level, alpha (1-sided)	2.50%	2.50%	2.50%
Noninferiority Margin for the SCR comparison (%)	10	10	10
Assumed true SCR	50%	50%	50%
Power for SCR comparison tests for each strain (%)	97.32%	97.32%	97.32%
Global Power for 4 SCR Endpoints	89.70%		
Noninferiority Margin for the GMT ratio	1.5	1.5	1.5
Common Standard Deviation of $\log_e(\text{titre})$	1.4	1.4	1.4
Power for GMT ratio tests for each strain (%)	99.99%	99.99%	99.99%
Global Power for 4 GMT ratio Endpoints	99.95%		
Global Power for 8 Co-primary Endpoints	89.66%		

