11.3.1.2 Subject Characteristics

At a minimum, subject characteristics will be presented in summary tables by treatment group, by age cohort and overall. Continuous data will be summarized by descriptive statistics (n, mean, median, minimum, maximum and standard deviation) and categorical data will be summarized by contingency tables (frequency and percentage). Age will be described as both a continuous and a discrete variable. All data will be listed by subject.

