### Primary Endpoints

Co-primary immunogenicity endpoints of GMT and SCR for each virus strain contained in the vaccine will be assessed among a pediatric population 6 through 59 months of age.

The rate of seroconversion is defined as the percentage of subjects with either a pre-vaccination hemagglutination inhibition (HI) titer < 1:10 and a post-vaccination HI titer  $\geq$  1:40 or a pre-vaccination titer  $\geq$  1:10 and a  $\geq$  4-fold increase in post-vaccination titer.

The non-inferiority of Seqirus QIV compared to the US-licensed comparator QIV will be assessed by the 8 co-primary endpoints of GMT and SCR.

In line with the FDA Guidance on seasonal inactivated influenza vaccines (*Guidance for Industry Clinical Data Needed to Support Licensure of Seasonal Inactivated Influenza Vaccines 2007*), Seqirus QIV will be considered to be non-inferior to the US-licensed comparator QIV if, for each of the four strains, the following statistical criteria are met:

- The upper bound of the two-sided 95% confidence interval (CI) on the ratio of the GMTs does not exceed 1.5. The GMT ratio will be calculated by GMT US-licensed comparator QIV / GMT Seqirus QIV
- The upper bound of the two-sided 95% CI on the difference between the SCRs does not exceed 10%. The difference in SCRs will be calculated by (Seroconversion US-licensed comparator QIV – Seroconversion Seqirus QIV). The 95% CI will be computed based on the binomial distribution.

To determine the GMT ratio (adjusted analysis) a general linear model (GLM) will be fitted on log transformed (natural log) post-vaccination HI titer as the outcome variable and terms for covariates: vaccine treatment, pre-vaccination HI titer, age stratum, gender, vaccination history, age-by-vaccine interaction and study site. Potential covariate interaction effects will also be examined in the fit of the GLM. From the model an adjusted difference in least square means (on the log scale) will be produced with 95% confidence limits. The estimated difference and the confidence limits will be back transformed to obtain an *adjusted* GMT ratio with 95% confidence limits. Each of the four strains will be analysed separately. The adjusted GMT ratio will be the result for which the non-inferiority assessment of the HI GMT co-primary endpoint will be based on.

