The complete set of covariates that will be used in the model to calculate the adjusted GMT ratio will include treatment group (2 treatments), pre-vaccination mean GMT titer (value), age strata (2 categories, 6 through 35 months or 36 through 59 months), gender (male or female), influenza vaccination received prior year (Yes or No), Number of Dose (1 vs 2), and investigator site (site identifier).

The GLM specification is:

- Adjusted Analysis GMT Model: Log-transformed Post-vaccination HI Titer = Vaccine + Age Strata + Gender + Vaccination History [y/n] + Log-transformed Pre-vaccination HI Titer + Site + Number of Dose [1/2] + Age Strata\*Vaccine.

For any strain, the interaction term *Age Strata\*Vaccine* will be removed from the fit of the model if it is assessed to be not significant.

The measure of the *unadjusted* GMT ratio based on post-vaccination GMTs only will also be presented.

The PPP will be the primary analysis population for the primary immunogenicity analysis and a supporting analysis may be performed using the evaluable population according to the criteria outlined in [Section 3.5.4](#).

If all 8 co-primary endpoints result in a conclusion of non-inferiority then overall non-inferiority of Seqirus QIV compared to the US-licensed comparator QIV will be concluded.

This assessment will be conducted overall (the primary endpoint).

In mathematical notation the statistical hypotheses to be tested for the primary immunogenicity analysis corresponds to:

H0:  $R_i > 1.5$ , for any strain

Ha:  $R_i \leq 1.5$ , for all strain

and

H0:  $D_i > 10$ , for any strain

Ha:  $D_i \leq 10$ , for all strain

where  $R_i$  is any of the 4 strain-specific post immunogenicity dose GMT ratios:

- (US-licensed comparator QIV) / (Seqirus QIV) for B/Yamagata strain
- (US-licensed comparator QIV) / (Seqirus QIV) for B/Victoria strain
- (US-licensed comparator QIV) / (Seqirus QIV) for A/H1N1 strain
- (US-licensed comparator QIV) / (Seqirus QIV) for A/H3N2 strain

and  $D_i$  is the 4 strain-specific post-dose SCR difference, namely

- (US-licensed comparator QIV) - (Seqirus QIV) for B/Yamagata strain
- (US-licensed comparator QIV) - (Seqirus QIV) for B/Victoria strain
- (US-licensed comparator QIV) - (Seqirus QIV) for A/H1N1 strain
- (US-licensed comparator QIV) - (Seqirus QIV) for A/H3N2 strain

No adjustment will be made for multiple comparisons.

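### With 3:1 allocation, the GMT-ratio limit from an apparently pooled-variance model keeps its stated one-sided 2.5% error only if residual titer spread is equal in both arms, and the plan has no safeguard for unequal spread

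*Protocol*

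**What the plan says.** The Protocol synopsis and section 11.3.2.1 fit a general linear model to log post-vaccination titer, with covariates for vaccine plus "prevaccination HI titer, age stratum, sex, vaccination history, age-by-vaccine interaction and study site". The limits are then obtained as follows: "From the model an adjusted difference in least square means (on the log scale) will be produced with 95% confidence limits". These are back-transformed, and the adjusted ratio (Comparator over Seqirus) carries the noninferiority decision. SAP 4.7.2 gives the criterion: "The upper bound of the two-sided 95% confidence interval (CI) on the ratio of the GMTs does not exceed 1.5".

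The SAP writes the model out as "Log-transformed Post-vaccination HI Titer = Vaccine + Age Strata + Gender + Vaccination History [y/n", continuing with log pre-vaccination titer, site, number of doses and the age-by-vaccine interaction. These are all terms for the mean. Neither document's readable text mentions a variance structure, a robust or Welch-type standard error, a check of equal variance, or a sensitivity analysis for unequal spread.

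On allocation, the synopsis says that "subjects will be randomized to one of the two treatment groups using a 3:1 allocation ratio". Each of the eight tests is planned "using a one-sided alpha of 0.025 for each comparison". The sample-size table (Protocol 11.1, repeated in SAP 3.9) has a single row, "Common Standard Deviation of" log titer, set to 1.4 for every strain. Overall noninferiority requires all eight co-primary endpoints to pass (Protocol 11.3.2.1, SAP 4.7.2).

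**The concern.** An ordinary general linear model estimates one residual variance from everyone. With 3:1 allocation that estimate is about three-quarters Seqirus data. The uncertainty of the difference sits mostly in the other arm: with equal SDs, the 500 comparator children contribute (1/500)/(1/500 + 1/1500) = 75% of its variance. If the comparator residuals are more spread out, the pooled standard error is too small and the upper limit too low, which favours noninferiority. If they are less spread out, the limit is too high and the test is conservative. With equal arms the two effects cancel.

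At stake are the one-sided 0.025 stated for each GMT comparison and the 95% coverage of the reported intervals. The relevant spread is what remains after adjustment for pre-vaccination titer, dose number, site and the other covariates, not the raw spread of titers.

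**Working it through.** **Inputs from the documents.** Evaluable 1500 Seqirus and 500 Comparator; margin 1.5 (ln 1.5 = 0.405465); SD of log titer 1.4; one-sided alpha 0.025. **Assumed, because the documents do not give it:** the ratio r of residual SDs, Comparator/Seqirus.

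**1. The plan's own figure.** SE = 1.4 × √(1/500 + 1/1500) = 0.0723. Power per strain = Φ(0.405465/0.0723 − 1.96) = 99.987%; to the fourth power, 99.947%. The plan states 99.99% and 99.95%, so these are reproduced. They use equal SDs.

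**2. Error of a pooled-variance limit when the true ratio is 1.5.** Set the Seqirus residual SD to 1:
- SE_model² = [(1500 + 500r²)/2000] × (1/1500 + 1/500)
- SE_true² = 1/1500 + r²/500
- one-sided error = Φ(−1.96 × SE_model/SE_true)

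Example, r = 1.2: the pooled variance is (1500 + 720)/2000 = 1.11. SE_model = √(1.11 × 0.0026667) = 0.0544 and SE_true = √(0.0006667 + 0.00288) = 0.0596. Their ratio is 0.914, so the error is Φ(−1.79) = 3.67%.

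| r | SE_model/SE_true | one-sided error | coverage of 95% CI |
|---|---|---|---|
| 0.8 | 1.117 | 1.43% | 97.1% |
| 0.9 | 1.054 | 1.94% | 96.1% |
| 1.0 | 1.000 | 2.50% | 95.0% |
| 1.1 | 0.954 | 3.08% | 93.8% |
| 1.2 | 0.914 | 3.67% | 92.7% |

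At 1000/1000 and r = 1.2, both variances equal 0.00244, so the error stays at 2.50%. The sensitivity to unequal spread therefore comes from the 3:1 allocation.

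**3. Check with covariates.** ANCOVA was simulated at a true ratio of 1.5 with 4000 runs per setting (Monte Carlo SE about 0.25 points), 30 sites and covariate effects assumed, and no interaction term. At r = 0.8, 1.0, 1.2 and 1.5, the ordinary limit gave errors of 1.35%, 2.6%, 3.25% and 4.8%. HC3 gave 2.2%, 2.5%, 2.2% and 2.2%.

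**4. Is any inequality plausible?** SAP 4.11 summarises titers below 10 as 5. At the noninferiority boundary Seqirus is the lower-titer arm, so more of its values sit on that floor and its spread shrinks. As an illustration, assume log-normal titers with underlying SD 1.4, a floored GMT ratio of exactly 1.5 and no covariates. At Seqirus GMTs of about 12, 17, 21 and 40, r is 1.13, 1.08, 1.06 and 1.02, and the error is 3.3%, 3.0%, 2.8% and 2.6%. Above a GMT of about 80 the effect disappears.

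**5. Power after the change.** With Seqirus SD 1.4 and comparator SD 1.4r, an unequal-variance limit has per-strain power of 99.99% at r = 1.0 and 99.8% at r = 1.2. For four strains, as a product, that is 99.95% and 99.3%.

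**The case against.** The strongest reply has four parts.

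**Pooling is not shown.** SAP 4.14 has an entry for analysis of covariance and between-arm intervals, but its code is redacted, and a group-variance or robust option would appear there. The Protocol's abbreviation list even expands GLM as generalized linear model, although its text says general. This stands as a limit: pooling is the normal reading of a general linear model given only by its mean terms, but it remains an inference.

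**Nothing in the documents shows unequal spread.** They assume a common SD. At r between 0.9 and 1.1 the error moves only from 1.9% to 3.1%, and the cases below 1 are conservative. This also stands. A reader might infer that the limit generally favours the sponsor; it does so only when the comparator residuals are the more variable.

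**The joint rule protects the overall conclusion.** A reader might infer that the trial would falsely declare noninferiority 3% to 4% of the time. The documents do not support that. Suppose spread differs because the vaccines differ in their share of responders, with an assumed 16-fold gain and within-group SD 0.8. A GMT ratio of 1.5 then needs a gap of ln 1.5/ln 16 = 14.6 points in responder share, and the same strain must also pass seroconversion with a 10-point margin. Simulated at Seqirus responder shares of 10% and 15%, with seroconversion taken as a rise of at least 4-fold, GMT alone passes in roughly 3.5% to 4% of trials, but GMT and seroconversion together in at most about 0.05%. In general, false overall success cannot exceed the error of any one truly inferior endpoint. It approaches that error only if a strain is inferior on GMT while the other endpoints, including its own seroconversion, pass comfortably.

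**Common-variance ANCOVA is a standard, prespecified choice.** That is true, and the plan contains no contradiction or wrong figure here. But the stated per-comparison error and the interval coverage still depend on an assumption that the readable text does not protect.

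A reader might also extend the criticism to the unadjusted GMT ratio. Its interval method is not stated, so no defect is shown there.

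**Conclusion.** The point holds as a cheap improvement to the primary GMT analysis. If the model pools the residual variance, as its description implies, its limit delivers one-sided 0.025 per comparison only when residual spreads are equal. Across assumed SD ratios of 0.9 to 1.1 the error is 1.9% to 3.1%, and at 1.2 it is 3.7%. Only a more variable comparator arm pushes it above 2.5%. The floor rule in SAP 4.11 makes a mild inequality in that direction plausible for low-titer strains, at about 2.6% to 3.3% under the log-normal illustration.

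The demonstrated effect is on per-endpoint error and interval coverage. It is not shown that the overall noninferiority conclusion would be materially wrong, and the sample size is unaffected.

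**What to change.** In Protocol 11.3.2.1, the synopsis and SAP 4.7.2, keep the model and its covariates. State that the 95% limits of the adjusted GMT ratio are computed with residual variances estimated separately by vaccine group, or with an HC3 standard error. At minimum, prespecify this as a sensitivity analysis, fixed before unblinding so that the choice of standard error cannot follow the data. Also state the variance assumption in the text.

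The cost is one sentence and one software option, with no added subjects or data. If spreads are equal, the interval widens by under 1%. For HC3 with 36 model parameters (30 sites assumed; the documents do not give the number), 36/2000 = 1.8% of variance, or about 0.9% of the standard error. GMT power stays at about 99.95% for four strains.

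Optionally, add age in months beside the age-stratum term. Age is already summarised both ways (Protocol 11.3.1.2: "Age will be described as both a continuous and a discrete variable"), which is a descriptive provision and not an inconsistency with the model. The gain is minor and unproven. If the partial correlation with log titer within stratum were 0.1 to 0.3 (assumed), the interval would narrow by 1 − √(1 − ρ²), or 0.5% to 4.6%, which matters little at 99.99% power per strain.
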